8.2 Severity of Adverse Event

The severity of each AE will be graded using the following criteria:

Grade	Description
1	Mild - Minor AEs requiring no specific medical intervention including
	asymptomatic laboratory findings only, or findings of marginal clinical relevance.
2	Moderate - AEs requiring minimal, local, and/or noninvasive intervention.
3	Severe - Severe and undesirable AEs involving significant symptoms requiring
	hospitalization or invasive intervention; transfusion; elective interventional radiological procedure; or therapeutic endoscopy or operation.
4	Life-threatening or debilitating - AEs complicated by acute, life-threatening metabolic or cardiovascular complications such as circulatory failure, hemorrhage, or sepsis. Also, life-threatening physiologic consequences; need for intensive care or emergent invasive procedure; emergent interventional
	radiological procedure, therapeutic endoscopy or operation.
5	Death

If the Grade changes within a day, the maximum Grade shall be recorded. If the Grade changes over a longer period of time, the changes shall be recorded as separate events (having separate onset and stop dates for each grade).

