Methodology: Subjects will be patched with a test material, a positive control and a negative control 10 times over 40 days, 9 during Induction Phase and 1 during Challenge Phase. Each patch will be worn for approximately two days. Before each patch application, the test site will be evaluated using the Erythemal Scoring Scale (ESS) and Additional Reaction Scoring. Following a Rest Phase of approximately 10 to 14 days, the subjects will again be patched on a virgin test site with the test material (but not the negative control nor the positive control). After two days of skin contact, the test sites will be evaluated using the ESS and Additional Reaction Scoring on removal day and Days 1 and 2 post-removal. The ESS and Additional Reaction Scoring results will be evaluated to determine the allergic potential of the test material. The three test sites will be as follows: test material; saline negative control; and positive control (0.4% SLS).

Number of Subjects Planned and Analyzed: Approximately 57 subjects will be enrolled in the trial so that at least 50 subjects will complete the trial. Data from all subjects who complete the Induction Phase will be analyzed for irritant contact dermatitis potential. Data from all subjects who complete the Challenge Phase will! be analyzed for allergic contact sensitization potential.

[figure not shown]
Diagnosis and Main Criteria for Inclusion: Healthy adult male and non-pregnant females aged 18-79 years, inclusive.

Test Material, Dose and Mode of Administration, Batch Number: The test material, approximate 8 mm disc of NeoMatriX™, will be applied to the cotton pad of each patch. Patches consisting of the test material and controls will be applied to specific test sites on the back of each subject.

Duration of Treatment: Fresh patches of test material and controls during the Induction Phase (approximately 3 weeks); no patches during the Rest Phase (approximately 2 weeks); and one patch of test material during Challenge Phase (approximately 1 week). No negative control nor positive control will be applied during the Challenge Phase.

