Criteria for Evaluation: Irritant contact dermatitis potential and allergic contact sensitization potential will be assessed through the evaluation of the test sites of application using the ESS and Additional Reaction Scoring. Statistical Methods: The ESS scores and Additional Reaction Scoring scores will be tabulated. The incidence of AEs, new-onset AEs, will be summarized. Maximum intensity and duration of AEs will be summarized by treatment group.

FLOW CHART OF TRIAL DESIGN

1 Background

A repeated insult patch test is a test devised to ascertain if an agent has the potential to cause contact irritation or contact allergy in the skin (Reference 12.1 and 12.2). Allergy is only elicited in immunologically competent individuals who have become sensitized through exposure to the agent following repeated cutaneous patch applications.

2 Trial Objective

The first primary objective of this trial is to determine by repetitive epidermal contact, the primary or cumulative irritation potential of a test material.

The second primary objective of this trial is to determine by repetitive epidermal contact, the allergic contact sensitization potential of a test material.

3 Proposed Schedule

Proposed trial initiation and termination dates will be established prior to the start of testing. The summary schedule of Induction Phase visits is shown in the table below.

[figure not shown]
Induction Phase Visits

The summary schedule of Rest Phase and Challenge Phase visits is shown in the table below.

K

, 3

Rest Phase and Challenge Phase Visits

4 Test Materials

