6.4.1 ESS

Erythema at the test site is evaluated according to the ESS shown below. Any score of 2 through 4 will be captured as an AE.

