6.4.2 Additional Reaction Scoring

If present, each additional reaction sequela is evaluated according to the following letter scale and a corresponding numerical scale to indicate severity shown below. Any Severity Score of 2 through 4 will be captured as an AE.

7 Statistical Methods

None anticipated.

8 Safety

An adverse event (AE) is any unfavorable and unintended sign, symptom, or disease that may or may not be considered related to the test material. This includes unfavorable or unintended change in body structure (signs), body function (symptoms), abnormal or severely altered laboratory result, or worsening of any pre-existing condition that occurs during the course of the trial.

Page: 15 of 21

Also, each subject will be carefully monitored for the development of any AEs. This information may be obtained from signs and symptoms detected during each examination, observations by the trial personnel or spontaneous reports from the subjects. This includes AEs resulting from concurrent illnesses, reactions to concomitant medications or progressive disease states.

All AEs, whether volunteered, elicited or noted during examination, shall be recorded on the subject's CRF using the Common Terminology Criteria for Adverse Events (CTCAE) v.4.

The PI will evaluate all AEs for their relationship to, or association with the test material (or other causes) and their intensity. Additionally, the actions taken (*e.g.*, reduction of test material concentration, discontinuation of test material application, administration of treatment, *etc.*) and the resulting outcome of the AE will be indicated on a CRF (*e.g.*, Sponsor, CPT, MedWatch or other appropriate Form).

Any subject who is withdrawn from the trial due to an AE will be followed until the outcome of the event is determined, and the PI will prepare a written summary of the event and document the available follow-up information on a CRF.

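### Do the adverse event tables need a rule linking grade changes, and a breakdown by patch site, written into the plan?

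*Combined protocol and SAP*

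**What the plan says.** Section 8.2 sets out how the grade of an AE is recorded. If the grade moves within one day, only the highest is kept. Otherwise: "If the Grade changes over a longer period of time, the changes shall be recorded as separate events", each with its own onset and stop date.

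The reporting plan is in the synopsis under Statistical Methods. It tabulates the scores on both skin scales and adds two sentences on AEs: "The incidence of AEs, new-onset AEs, will be summarized" and "Maximum intensity and duration of AEs will be summarized by treatment group". Section 7, Statistical Methods, contains only "None anticipated".

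Skin reactions become AEs through Section 6.4.1 ("Any score of 2 through 4 will be captured as an AE") and Section 6.4.2 ("Any Severity Score of 2 through 4 will be captured as an AE"). The synopsis gives each subject three test sites: test material, saline and the positive control, 0.4% SLS. Section 8.1 says that, in safety analyses, an AE rated possible or probable counts as related to the test material.

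**The concern.** Three things look wrong when these sections are read together.

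- **Counting unit.** Section 8.2 can turn one lasting reaction into several dated records, and nothing links them again. New-onset is not defined, and incidence could mean subjects or events. If each record were tabulated as an event, counts would rise and durations would fall with the number of grade changes.
- **Positive control.** SLS is applied to provoke irritation, yet the visible text makes a score of 2 to 4 at that site an AE like any other. The incidence sentence has no breakdown by site. The intensity and duration sentence uses treatment group, which is undefined when every subject is exposed to all three materials.
- **Unequal exposure.** If treatment group means material, the test material has a Challenge patch that the controls lack.

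At stake is whether a reader of the AE tables would see the test material's safety profile, or mainly recording habits and expected SLS reactions.

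**Working it through.** The plan states no AE rate, count or duration, so there is no figure to reproduce. The documents supply the number enrolled (about 57), nine Induction patches in 21 days with an evaluation before each, one Challenge patch of test material, and the Section 8.2 recording rule. Every rate and grade path below is an assumption.

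**Splitting.** A reaction lasting D days with k constant-grade phases gives k records of mean length D/k. For D = 7:

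| k | Records | Mean days (7/k) | Subjects affected |
|---|---|---|---|
| 1 | 1 | 7.0 | 1 |
| 2 | 2 | 3.5 | 1 |
| 3 | 3 | 2.3 | 1 |
| 4 | 4 | 1.8 | 1 |

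A six-day daily path of grades 1, 1, 2, 2, 1, 1 gives 3 records averaging 6/3 = 2 days. Its maximum grade is 2, whether it is read as one reaction or three records.

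Two facts limit k. First, the split follows the Section 8.2 grade, not the erythema score. Grade 3 there involves hospitalization or an invasive intervention, so patch reactions would mostly move between Grades 1 and 2. Second, nine evaluations in 21 days is 9/3 = 3 a week. Four phases need three changes, so k = 4 within a week would require a change at essentially every evaluation.

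The split can also be undone. Each record carries onset and stop dates, so consecutive records of one reaction in one subject can be joined end to end. That is a small task with about 57 subjects.

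**SLS.** Let pS and pT be the proportions of subjects with an AE at the SLS and test-material sites, taken as independent. Overall incidence is 1 − (1 − pS)(1 − pT), so a rise in pT of 8 points (2% to 10%) shows as (1 − pS) × 8 points.

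| pS | Subjects with an AE if pT = 0 (57 × pS) | Overall, pT = 2% | Overall, pT = 10% | Change (points) |
|---|---|---|---|---|
| 0% | 0 | 2.0% | 10.0% | 8.0 |
| 20% | 11.4 | 21.6% | 28.0% | 6.4 |
| 50% | 28.5 | 51.0% | 55.0% | 4.0 |
| 80% | 45.6 | 80.4% | 82.0% | 1.6 |

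The dilution is real for a single pooled figure. At the test-material site alone, the same rise is 57 × 0.02 = 1.1 to 57 × 0.10 = 5.7 subjects, whatever pS is. That information survives because the synopsis tabulates the scores themselves, and the reactions captured as AEs under Sections 6.4.1 and 6.4.2 are those same scores of 2 to 4.

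**Exposure.** The synopsis states: "No negative control nor positive control will be applied during the Challenge Phase". The test material therefore has 9 + 1 = 10 applications and each control 9. The opening sentence of the synopsis Methodology can be read as 10 for all three, and those statements must be reconciled for their own sake. No AE comparison between sites is tested, so the difference of one application biases no planned result.

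**Where the tables lead.** Irritation is judged from Induction scores and sensitization from Challenge scores (Section 6.1). Neither uses an AE count or an AE duration.

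**The case for a change.** The best case for a change is that safety tables are promised output, Section 7 gives no rule for them, and the wording is cheap to fix before data are collected. Three arguments support it.

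- Section 8.3 makes repeated occurrences of an AE, judged in aggregate, a ground for telling the IRB, so occurrences need a unit.
- The Section 8.1 subset may not remove SLS reactions. Test and control patches are worn over the same weeks, so an SLS reaction could meet the criteria for a possible relationship and be counted as related to the test material.
- Section 8 defines an AE as unintended, which sits awkwardly with capturing every score of 2 to 4 at a site meant to react.

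Part of this stands. The counting unit, new-onset and treatment group are undefined, and in the visible text SLS scores of 2 to 4 do enter overall incidence. Section 8.1 separates the sites only partly.

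The rest carries less weight. The IRB criterion asks for a judgement that the events are more than isolated occurrences, and grade phases of one reaction would not reasonably be taken as a series. A test-material reaction can be told from an SLS reaction by where the patch was, which the site scores must show if the trial is to assess the test material at all. The text on controls and the Induction procedure is not visible, so an exemption there cannot be excluded.

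**Conclusion.** No change to the plan is needed. The documents leave three terms undefined for descriptive AE tables. Section 8.2 is a recording rule, and no text says that incidence or duration is computed per record. If records were nevertheless tabulated one by one, event counts would be multiplied by k and mean duration divided by k. How often k exceeds 1 is unknown, and subjects affected and maximum grade would not move. Overall incidence could be dominated by SLS reactions only under assumed SLS rates, which the documents do not give. The score tables, a by-material reading of treatment group and the Section 8.1 subset would still show the test material separately, at least in part.

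An analyst would ordinarily count subjects, join the records of one reaction, and label site reactions by material. The three terms can be stated in table footnotes in the report. The tables feed no test and no decision rule, and both primary assessments rest on the site scores, so no conclusion of the trial would differ. This rests on the scores being kept by site, which the design requires, and on the visible text only.

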8.3 Serious Adverse Events

The PI will evaluate all serious AEs as to their intensity, relation to test material, outcome, and action taken. An SAE is defined as any AE that suggests a significant clinical hazard, contraindication, side effect, or precaution. This includes any event which:

- · Results in death;
- Is life-threatening;
- · Results in persistent or significant disability/incapacity;
- Results in or prolongs an existing inpatient hospitalization;
- Results in a congenital anomaly/birth defect;
- Is an important medical event based on medical judgment, which jeopardizes the subject and requires medical or surgical intervention to prevent one of the outcomes listed above.

ANY SAE, INCLUDING DEATH DUE TO ANY CAUSE, WHICH OCCURS DURING THE TRIAL, WHETHER OR NOT RELATED TO THE TEST MATERIAL, MUST BE REPORTED TO THE SPONSOR OR MEDICAL MONITOR WITHIN 24 HOURS OF WHEN THE PI BECAME AWARE OF THE SAE.

[name] [contact]

The PI must complete an AE form and send the form to the Medical Monitor or Sponsor within 24 hours of when the PI became aware of the SAE.

CPT may supply MedWatch Forms for SAE reporting, but the responsibility for reporting SAEs to FDA rests with the Sponsor or Medical Monitor. If additional information regarding a previously submitted SAE is obtained, a follow-up SAE report will be completed and sent to the Sponsor or Medical Monitor as indicated above. A copy of safety reports that are filed with the FDA will be sent to each PI participating in any ongoing trials the Sponsor is : 湖: conducting with the same test material.

17 of 21

The PI will promptly notify the IRB for only the following AEs.

· A single occurrence of a serious event that is uncommon and strongly associated with drug exposure.

- A single occurrence, or more often a small number of occurrences of a serious, event that is not commonly associated with drug exposure, but uncommon in the clinical trial populations.
- Multiple occurrences of an AE that, based on an aggregate analysis, is determined to be an unanticipated problem. There should be a determination that the series of AEs represents a signal that the AEs were not just isolated occurrences and involve risk to human subjects.
- · An SAE that is described in the investigator's brochure, protocol, or informed consent documents, but occurs at a specificity that is inconsistent with prior observations.
- An SAE that is described or addressed in the investigator's brochure, protocol or informed consent documents, but for which the rate of occurrence in the trial represents a clinically significant increase in the expected rate of occurrence,
- Any other AE or safety finding that would cause the sponsor to modify the investigator's brochure, clinical trial protocol, or informed consent documents, or would prompt other action by the IRB to ensure the protection of human subjects.

8.4 Management of Adverse Events

All AEs will be reported from the time a signed and dated informed consent form is obtained until completion of the last trial-related procedure. Those AEs meeting the definition of SAEs must be reported using the Adverse Event Form, including SAEs spontaneously reported to the PI within 30 days after the subject has completed the trial (including post-trial follow up). The Sponsor assumes responsibility for appropriate reporting of adverse events to the appropriate regulatory authorities.

All pregnancies occurring during clinical trials must be reported to the Sponsor, or its designee, by the PI within 24 hours of observation or notification of the occurrence. All efforts should be made to obtain follow-up information regarding the outcome of pregnancy and any postnatal sequelae in the infant. Although the occurrence of pregnancy is not an SAE, complications or serious outcomes of the pregnancy must be reported as appropriate. Events that meet the criteria for an SAE must be reported. Pregnancy is considered an exclusion criterion in this trial. Any trial subject who becomes pregnant during trial participation must promptly discontinue further administration of the test material.

Symptomatic treatment of suspected AEs shall be initiated as medically indicated. Any such treatment must be recorded on the CRF. Interruption or discontinuation of test material application may also be required in some circumstances. Causes of AEs other than the trial test material (such as intercurrent illness, other medications, or treatments) shall be excluded before adjustment, interruption, or discontinuation of the trial test material. If there is doubt concerning the cause of a serious or potentially serious AE, exposure to the trial test material shall be discontinued.

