5.4 Withdrawal of Subjects

The subject is free to withdraw their consent to participate in the trial at any time and for any reason, in accordance with the principles of the World Medical Association Declaration of Helsinki (as amended) and of the Belmont Report. The PI also has the right to withdraw a subject from the trial for safety, lack of efficacy or administrative reasons.

Possible reasons why a subject may be withdrawn from the trial include the following:

- 1. Experiences a serious or intolerable AE;
- 2. Develops, during the course of the trial, symptoms or conditions listed in the exclusion criteria, including pregnancy;
- 3. Takes medications that are contraindicated, as described in the exclusion criteria;
- 4. Incurs a protocol violation such as failure to comply with the specified treatment regimen or failure to comply with the visit schedule; or
- 5. Requests an early discontinuation due to:
 - A clinical reaction for which the PI did not consider removal from the trial to be necessary;
 - Other (non-specific) subject-initiated reason

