8.1 Relationship to Test Materials

The relationship or association of the AE to a test material will be characterized as unlikely, possible or probable (Reference 12.3). Assessments shall be recorded on the CRF.

Causality Term	Assessment Criteria
Probable	Event or laboratory test abnormality, with plausible time relationship to test material intake
	Unlikely to be attributed to condition (or disease) or other products in use by subject
	Response to withdrawal clinically reasonable
	Rechallenge satisfactory or not required
Possible	Event or laboratory test abnormality, with reasonable time relationship to test material intake
	Could also be explained by condition (or disease) or other products in use by subject
	Response to withdrawal unclear or lacking
Unlikely	Event or laboratory test abnormality, with a time to test material intake that makes a relationship improbable (but not impossible)
	Condition (or disease) or other products provide plausible explanations

For safety analyses, AEs that are classified as a possible or probable association to a test material shall be considered test material-related AEs.

Follow-up of the AE, after the date of discontinuation of exposure to test material is required if the AE or its sequelae persist. Follow-up is required until the event or its sequelae resolve or stabilize at a level acceptable to the PI and to the Medical Monitor.

16 of 21

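### Read literally, Section 8.4 bars interrupting patches for a non-serious AE until other causes are excluded, which conflicts with 5.4; subjects stopped for a reaction would also leave the irritation analysis

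*Combined protocol and SAP*

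**What the plan says.** Section 8.4 (Management of Adverse Events) first allows that stopping may be needed: "Interruption or discontinuation of test material application may also be required in some circumstances". It then sets a condition. Causes other than the test material, such as intercurrent illness or other medications, "shall be excluded before adjustment, interruption, or discontinuation of the trial test material". The next sentence covers doubt, but only for one class of event: "If there is doubt concerning the cause of a serious or potentially serious AE, exposure to the trial test material shall be discontinued". Pregnancy has its own stop rule in the same section.

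Section 5.4 (Withdrawal of Subjects; two sections carry the number 5.4) sets no causality condition: "The PI also has the right to withdraw a subject from the trial for safety, lack of efficacy or administrative reasons". Its list of possible reasons begins with "Experiences a serious or intolerable AE".

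On analysis, the synopsis plans about 57 subjects so that at least 50 complete, and assigns the irritation analysis to subjects who complete the Induction Phase. Section 7 (Statistical Methods) anticipates none, so nothing there brings back a subject whose patching was stopped during Induction.

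**The concern.** Non-serious skin reactions are what this trial is built to detect. Sections 6.4.1 and 6.4.2 make any erythema or additional-reaction score of 2 to 4 an AE, and healthy volunteers are patched 9 times in 21 days. If the 8.4 sentence is followed as written, a reaction that is not serious and whose cause is unclear could be patched again while other explanations are worked up. The PI would also hold two instructions that disagree: one allows withdrawal for an intolerable AE, the other forbids stopping the material until other causes are ruled out.

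There is an analytic consequence as well. Making it easier to stop patching, as safety requires, makes it more likely that a reacting subject fails to complete Induction. Under the synopsis rule that subject leaves the irritation analysis. Those lost would be the most informative about irritation, so the bias runs toward finding none.

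**Working it through.** **Part 1: consistency of the text.** No calculation applies. Take a test-site reaction that the subject cannot tolerate, that is not serious or potentially serious, and whose cause is uncertain.

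1. Section 5.4 (Withdrawal of Subjects): intolerable stands as an alternative to serious, so this event is a listed reason for withdrawal. The PI may also act on safety grounds generally. Withdrawal ends patching, so stopping is permitted.
2. Section 8.4, exclusion sentence: it is mandatory and has no severity limit. Other causes have not been excluded, so its condition for stopping is unmet.
3. Section 8.4, next sentence: it applies only to serious or potentially serious AEs, so it gives no relief here.
4. Result: 5.4 permits what the literal text of 8.4 forbids.

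Now suppose that the same reaction is tolerable and the PI wants only to miss a patch or two and watch. Section 5.4 does not help, because it deals with leaving the trial. Section 8.4 names interruption explicitly and makes it subject to the same condition. The lesser step is therefore the one left with no clear authority.

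**Part 2: why the fix needs an analysis sentence.**

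Inputs from the synopsis: about 57 enrolled, at least 50 to complete, irritation analysed in Induction completers.

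Assumptions, for illustration only: r subjects react and are all stopped in Induction, nobody else reacts, and there is no other dropout. The range for r is 0 to 57 − 50 = 7, the planned allowance for non-completion.

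Formulas: completers n = 57 − r, showing 0/n reactors, with one-sided 95% upper bound 1 − 0.05^(1/n). With stopped reactors kept, the proportion is r/57.

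| r | Completers only | Upper bound | Stopped reactors kept |
|---|---|---|---|
| 0 | 0/57 | same data | 0/57 = 0% |
| 1 | 0/56 | 1 − 0.05^(1/56) = 5.2% | 1/57 = 1.8% |
| 3 | 0/54 | 1 − 0.05^(1/54) = 5.4% | 3/57 = 5.3% |
| 7 | 0/50 | 1 − 0.05^(1/50) = 5.8% | 7/57 = 12.3% |

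The completer column shows no reactors whatever r is, and its bound barely moves. At r = 7 the proportion with reactors kept is about twice the completers' upper bound. The bounds are added here for scale; the plan specifies no interval.

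**The case against.** The best reply is that the sentence is clumsy and has little practical effect. Its likely intent is that the PI consider other causes first. Several routes stay open. The PI can withdraw the subject under 5.4, and the subject can leave at any time. The SAE definition in 8.3 is broad enough to bring some worrying reactions under the stop rule. Section 11.5 lets the PI depart from the protocol without prior sponsor approval to remove an apparent immediate hazard, with written notice within 5 working days. The Induction procedure in 6.3 is not visible in the text reviewed and may hold a rule for reacting sites. All of this stands, and it keeps the point minor. It does not remove the conflict with 5.4, and none of the visible routes clearly covers a simple interruption for a tolerable, non-serious reaction.

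A reader might also infer that 8.4 contradicts Section 8.1 and the opening of Section 8. The documents do not support that.

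- Section 8.1 classifies causality. A possible AE is one that "Could also be explained by condition (or disease) or other products in use by subject", but the rule counting such events as related is for safety analyses and does not govern when patching stops.
- The use of response to withdrawal in 8.1 does not presuppose early stopping. Each patch comes off after about two days and a patch-free Rest Phase follows Induction, so the response to removal can be seen anyway. The possible category also includes "Response to withdrawal unclear or lacking", which allows for cases with no such response to judge.
- Section 8 lists "discontinuation of test material application, administration of treatment" among example actions to record on a CRF. Recording an action is compatible with a condition on taking it.

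On the analysis, it is fair to say that stopped reactors would not vanish. Scores of 2 to 4 are captured as AEs and the synopsis summarises AE incidence. Section 5.5 asks for final-visit evaluations after withdrawal. Section 8 requires a written summary for a subject withdrawn because of an AE. This offsets the bias only in part: the irritation analysis, which serves a primary objective, would still omit those subjects.

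**Conclusion.** The point holds as a minor one. The exclusion sentence in 8.4 conflicts with 5.4 (Withdrawal of Subjects) for a non-serious AE of uncertain cause, and literally bars interrupting patches in that case. The documents do not support the inference that subjects will in fact be kept on patches against the PI's judgement. Any extra exposure due to 8.4 cannot be quantified from them, and no figure is claimed.

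The completers rule in the synopsis is a separate, related weakness that matters more once stopping is made easier. Its direction is toward no irritation. Its size depends on r, which is unknown. The contrast of 0/54 with 5.3% at r = 3 assumes that every reactor is stopped and no completer reacts, so it is an extreme illustration and not an estimate. If no one is stopped for a reaction, the rule costs nothing through this route.

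**What to change.** Two sentences, in one protocol amendment.

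1. Replace the exclusion sentence in 8.4 with: *Other causes of AEs will be evaluated, but need not be excluded before the PI interrupts or discontinues test material application for safety.* Keep the following sentence on serious or potentially serious AEs. When to stop remains the PI's clinical judgement.
2. Add beside the synopsis statement on subjects analysed, and in Section 7: *Subjects whose patching is interrupted or stopped for a test-site reaction are kept in the irritation tabulation with their scores up to that point, and their shorter exposure is shown.*

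This adds no visits or staff. The downside is that a few subjects will have fewer than 9 Induction patches, so their cumulative exposure is shorter and the tabulation must show it. Subjects who stop altogether also draw on the allowance of 57 − 50 = 7 non-completers (7/57 = 12.3%), which has to cover every other reason for dropout.
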